6.2 Toxicity Management

The toxicity management of the AEs including AESIs consists of safety monitoring (review of AEs on an ongoing basis) and, if applicable, interruption of study drug dosing with appropriate clinical management and/or discontinuation of the subjects from study drug. The management of specific AEs and laboratory parameters is described below.

Serious Infections: Study drug should be interrupted if a subject develops a serious infection. A subject who develops a new infection during treatment with study drug should undergo prompt diagnostic testing appropriate for an immunocompromised subject. Study drug may be restarted once the infection has been successfully treated. Subjects who develop active TB must be permanently discontinued from study drug.

Herpes zoster: If a subject develops herpes zoster, consider temporarily interrupting study drug until the episode resolves.

Gastrointestinal Perforation: If a diagnosis of gastrointestinal perforation is confirmed (other than due to appendicitis or mechanical injury), the subject must be permanently discontinued from study drug.

Major cardiovascular event: For subjects who develop a major cardiovascular event (MACE: acute myocardial infarction, stroke) while on study drug, the investigator should evaluate the benefit/risk of, and discuss with the TA MD, whether it is appropriate to continue study drug.

Malignancy: Subjects who develop malignancy other than localized NMSC or carcinoma in situ of the cervix must be permanently discontinued from study drug. Information including histopathological results should be queried for confirmation of the diagnosis. Periodic skin examination is recommended for subjects who are at increased risk for skin cancer. Subjects who develop malignancies should be referred to appropriate specialists and managed as per standard of care.

Muscle-related symptoms: If a subject experiences symptoms suggestive of myositis or rhabdomyolysis, consider checking CPK and aldolase with clinical management and/or study drug interruption as deemed appropriate by the investigator.

Thrombosis Events: Subjects who develop symptoms of thrombosis should be promptly evaluated and treated appropriately. If the diagnosis of deep vein thrombosis (DVT), pulmonary embolus or non-cardiac, non-neurologic arterial thrombosis is confirmed, the subject must be discontinued from study drug.

COVID-19: Interrupt study drug in subjects with a confirmed diagnosis of COVID-19. Consider interrupting study drug in subjects with signs and/or symptoms and suspicion of COVID-19. Study drug may be restarted if fever is resolved without use of antipyretics for 24 hours and other symptoms improved, or if 5 days have passed since the COVID-19 positive test result (whichever comes last). The COVID-19 eCRF must be completed.

Management of Select Laboratory Abnormalities: For any given laboratory abnormality, the investigator should assess the subject, apply the standard of care for medical evaluation and treatment following any local guidelines. Specific toxicity management guidelines for abnormal laboratory values are described in Table 3, and may require a supplemental eCRF to be completed. For subjects with ongoing laboratory abnormalities which require data entry into an eCRF, an additional eCRF related to subsequent laboratory abnormalities is only required if the subject has relevant changes in history (e.g., new onset signs or symptoms) or laboratory values which have returned to normal reference range or its Baseline value followed by subsequent laboratory abnormalities meeting toxicity guidelines (considered a new event). All abnormal laboratory tests that are considered clinically significant by the investigator will be followed to a satisfactory resolution. If a repeat test is required per Table 3, the repeat testing is to occur as soon as possible.

Table 3. Specific Toxicity Management Guidelines for Abnormal Laboratory Values

Laboratory Parameter	Toxicity Management Guideline
Hemoglobin	 If hemoglobin < 8 g/dL interrupt study drug dosing and confirm by repeat testing with a new sample. If confirmed, continue to withhold study drug until hemoglobin value returns to ≥ 8 g/dL. OR
	 If hemoglobin decreases ≥ 3.0 g/dL from Baseline without an alternative etiology, interrupt study drug dosing and confirm by repeat testing with new sample.
	 If hemoglobin decreases ≥ 3.0 g/dL from Baseline and an alternative etiology is known or the hemoglobin value remains in the normal reference range, the subject may remain on study drug at the investigator's discretion.
	 If confirmed, continue to withhold study drug until hemoglobin value returns to within 3.0 g/dL from Baseline.
Absolute neutrophil count (ANC)	 If confirmed < 1000/μL by repeat testing with new sample, interrupt study drug dosing until ANC value returns to ≥ 1000/μL.
	 For confirmed < 500/µL, if value returns to ≥ 1000/µL, restarting study drug is allowed if there is an alternative etiology identified; documentation should include reason that rechallenge is expected to be safe for the subject. Study drug should be discontinued if no alternative etiology can be found.
Absolute lymphocyte counts (ALC)	 If confirmed < 500/μL by repeat testing with new sample, interrupt study drug dosing until ALC returns to ≥ 500/μL.
Total white blood cell count	 If confirmed < 2000/μL by repeat testing with new sample, interrupt study drug dosing until white blood cell count returns to ≥ 2000/μL.

Laboratory Parameter	Toxicity Management Guideline
AST or ALT	Interrupt study drug if any of the following scenarios are confirmed by repeat testing of AST/ALT:
	 ALT or AST > 3 × ULN and either a total bilirubin > 2 × ULN or an international normalized ratio (INR) > 1.5:
	 A separate blood sample for INR testing will be needed to measure INR at the time of repeat testing for ALT or AST. A repeat test of INR is not needed for determination if above toxicity management criteria are met.
	 If a creatine phosphokinase (CPK) value is not available, a CPK should be drawn to exclude AST/ALT elevations related to muscle injury.
	 ALT or AST > 3 × ULN along with new appearance of fatigue, nausea, vomiting, right upper quadrant pain or tenderness, fever, rash, and/or new-onset eosinophilia.
	 ALT or AST > 5 × ULN for more than 2 weeks.
	If ALT or AST > 8 × ULN, interrupt study drug immediately, repeat testing with a new sample, and if repeat test confirms result, contact the TA MD.
	Subjects with HBc Ab+ (irrespective of HBs Ab status) and negative HBV DNA PCR testing at Screening who develop the following laboratory findings should have HBV DNA PCR testing performed within 1 week (based on initial elevated value):
	ALT> 5 × ULN OR
	 ALT or AST > 3 × ULN if an alternative cause is not readily identified.
	A separate blood sample for HBV DNA PCR testing will be needed at the time of repeat testing for ALT or AST.
	A positive result for HBV DNA PCR testing will require immediate interruption of study drug (unless not acceptable by local practices). Within one week of the first episode of a positive HBV DNA PCR test, a hepatologist consultation should occur for recommendation regarding subsequent treatment.
	Subjects who meet any of the above criteria should be evaluated for an alternative etiology of the ALT or AST elevation and managed as medically appropriate. If applicable, the alternative etiology should be documented in the eCRF. If ALT or AST values return to the normal reference range or its Baseline value, study drug may be restarted. If restarting study drug, documentation should include reason that rechallenge is expected to be safe. If after clinically appropriate evaluation, no alternative etiology for ALT or AST elevation is found or the ALT or AST elevation has not resolved or is not trending down toward normal, the subject should be discontinued from study drug.
	For any confirmed ALT or AST elevations > 3 ULN, complete the appropriate supplemental hepatic eCRF(s).

Laboratory Parameter	Toxicity Management Guideline
Serum Creatinine	If serum creatinine is > 1.5 × the Baseline value and > ULN, repeat the test for serum creatinine (with subject in an euvolemic state) to confirm the results. If the results of the repeat testing still meet this criterion, interrupt study drug and re-start study drug once serum creatinine returns to \leq 1.5 x Baseline value. For the above serum creatinine elevation scenario, complete the appropriate supplemental renal eCRF(s).

ALC = Absolute lymphocyte count; ALT = alanine transaminase; ANC = Absolute neutrophil count; AST = aspartate transaminase; DNA = deoxyribonucleic acid; eCRF = electronic case report form; HBc Ab+ = Hepatitis B core antibody positive; HBs Ab = Hepatitis B surface antibody; HBV = Hepatitis B virus; INR = international normalized ratio; OR = odds ratio; PCR = Polymerase chain reaction; TA MD = Therapeutic Area Medical Director; ULN = upper limit of normal

Elective and Emergency Surgeries

For elective and emergency surgeries the following rules will apply:

- If the subject must undergo emergency surgery, the study drug should be interrupted at the time of the surgery. After emergency surgery, allow reintroduction of study drug once the physician has examined the surgical site and determined that it has healed and there is no sign of infection.
- Elective surgery, and interruption of study drug for such a surgery, will not be allowed during the study until the primary endpoint has been assessed (Week 24). If elective surgery is considered prior to the primary endpoint visit (Week 24), it must be discussed with the TA MD and performed with TA MD approval. If the subject undergoes elective surgery, the study drug should be interrupted at least 1 week prior to the planned surgery. Allow reintroduction of study drug once the physician has examined the surgical site and determined that it has healed and there is no sign of infection.

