5.5 Withdrawal of Subjects and Discontinuation of Study

AbbVie may terminate this study prematurely, either in its entirety or at any site. The study may be discontinued or terminated in case of an unacceptable risk, any relevant toxicity, or a negative change in the risk/benefit assessment. This might include the occurrence of AEs with a character, severity or frequency that is new in comparison to the existing risk profile. In addition, data deriving from other clinical trials or toxicological studies which negatively influence the risk/benefit assessment might cause discontinuation or termination of the study. The investigator may also stop the study at their site if they have safety concerns. If AbbVie terminates the study for safety reasons, AbbVie will promptly notify the investigator. Advance notice is not required by either party if the study is stopped due to safety concerns.

Subjects can request to be discontinued from participating in the study at any time for any reason. The investigator may discontinue any subject's participation at any time for any reason.

Subjects must have study drug discontinued immediately if any of the following occur:

- The subject requests withdrawal from study drug or the study.
- The investigator believes it is in the best interest of the subject.
- Abnormal laboratory results or AEs that either meet the criteria for discontinuation of study drug as stated in Section 6.2, or rule out safe continuation of the study drug.
- Serious infections (e.g., sepsis) which cannot be adequately controlled by anti-infective treatment or would put the subject at risk with continuation of the study drug.
- Confirmed diagnosis of deep vein thrombosis (DVT), pulmonary embolus (PE) or non-cardiac, non-neurologic arterial thrombosis.

- Subject is non-compliant with TB prophylaxis (if applicable) or develops active TB at any time during the study.
- Malignancy, except for localized NMSC or carcinoma in-situ of the cervix if this can be successfully treated at its localization
- Subject develops a gastrointestinal perforation (other than due to appendicitis or mechanical injury).
- The subject experiences a serious hypersensitivity reaction without an alternative etiology.
- The subject becomes pregnant while on study drug.
- Eligibility criteria violation was noted after the subject started study drug, when continuation of the study drug would place the subject at risk.

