5.6 Follow-Up After Subject Discontinuation of Study Drug or From Study

Discontinuation of Study Drug

Following discontinuation of study drug, the subject should be treated in accordance with the investigator's best clinical judgment based on the available approved treatment options within their country or region.

Subjects who prematurely discontinue study drug treatment will be discontinued from study participation entirely.

If a subject prematurely discontinues study drug, the procedures outlined for the Premature Discontinuation visit (PD Visit) should be completed as soon as possible, preferably within 2 weeks, and preferably prior to initiation of another therapy. In addition, a 30-Day Follow-up Visit after the last dose of study drug is required to ensure all treatment-emergent AEs/SAEs have been resolved. For subjects who prematurely discontinued study participation, this visit may be a telephone call if a site visit is not possible. A follow-up phone call following the last dose of upadacitinib during the study will not occur for subjects who begin commercially available upadacitinib.

Premature Discontinuation of Study (Withdrawal of Informed Consent)

If a subject prematurely discontinues study participation (withdrawal of informed consent) the procedures outlined for the Premature Discontinuation visit (PD visit) should be completed as soon as possible, preferably within 2 weeks and preferably prior to initiation of another therapy. In addition, if the subject is willing, a 30-day follow-up phone call after the last dose of study drug may be completed to ensure all treatment-emergent AEs/SAEs have been resolved. The follow-up phone call following the last dose of upadacitinib during the study will not occur for subjects who begin commercially available upadacitinib.

For subjects to be considered lost to follow-up, reasonable attempts must be made to obtain information on the subject's final status. At a minimum, 2 telephone calls must be made and 1 certified letter must be sent and documented in the subject's source documentation.

If a subject withdraws from study follow up or withdraws permission for the collection of their personal data, the study staff may still use available public records to obtain information about survival status only, as appropriate per local regulations.

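### The ALT/AST restart rule in Table 3 leaves out the alternative-etiology condition, so a resolved but unexplained elevation is covered by both a permission to restart and a direction to stop.

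*Protocol*

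**What the plan says.** The last part of the ALT/AST row in Table 3 (Protocol Section 6.2) applies to every subject who meets one of that row's hepatic criteria. It gives these instructions, in this order:

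- Evaluate the subject for an alternative etiology and, if applicable, record it.
- "If ALT or AST values return to the normal reference range or its Baseline value, study drug may be restarted".
- When dosing resumes, the site has to write down why it considers re-exposure safe.
- After appropriate evaluation, stop study drug if "no alternative etiology for ALT or AST elevation is found or the ALT or AST elevation has not resolved", or if the elevation is not trending down toward normal.

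The ANC row of the same table handles a confirmed count below 500/µL differently. Once the count is back to 1000/µL or more, "restarting study drug is allowed if there is an alternative etiology identified", again with a documented reason. It then adds: "Study drug should be discontinued if no alternative etiology can be found".

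Section 5.5 opens its list with "Subjects must have study drug discontinued immediately if any of the following occur" and includes "Abnormal laboratory results or AEs that either meet the criteria for discontinuation of study drug as stated in Section 6.2". Section 5.6 sets the consequence: "Subjects who prematurely discontinue study drug treatment will be discontinued from study participation entirely".

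**The concern.** The restart sentence depends only on the laboratory value. The discontinuation sentence joins its triggers with *or*, so the absence of an alternative etiology is enough on its own, even after full resolution. The two sentences therefore overlap, and neither says which prevails.

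The overlap falls on a sensitive case. When ALT or AST normalises off drug and no other cause is found, study drug is hard to exclude as the cause. Protocol Section 2.2 lists transaminase elevations among the changes seen with upadacitinib, and Section 6.1 makes hepatic disorder an event of special interest. The criteria feeding this paragraph include ALT or AST above 3 × ULN with total bilirubin above 2 × ULN, close to the combination that SAP Section 10.3 and Table D-3 use to look for possible Hy's law cases.

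The restart sentence also comes before the sentence that refers to completed evaluation. A site working through the cell in order could restart on normal values while the work-up is still open.

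**Working it through.** The plan states no figure on this point, so the check is one of logic, followed by a short calculation of what the fix costs.

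**Step 1. Apply the ALT/AST sentences to each case.**

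| Elevation resolved? | Alternative etiology found? | Restart sentence | Discontinuation sentence | Result |
|---|---|---|---|---|
| Yes | Yes | Permits | Not triggered | Consistent |
| Yes | No | Permits | Triggered | Conflict |
| No | Yes | Does not permit | Triggered | Consistent |
| No | No | Does not permit | Triggered | Consistent |

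One case of the four falls under both instructions.

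**Step 2. Compare with the other resumption rules in Table 3.**

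| Rule | Condition to resume | Discontinue if no etiology found? |
|---|---|---|
| Hemoglobin < 8 g/dL | Value only | No |
| Hemoglobin fall ≥ 3.0 g/dL | Value only | No |
| ANC < 1000/µL | Value only | No |
| ANC < 500/µL | Value and alternative etiology, with documented reason | Yes |
| ALC < 500/µL | Value only | No |
| WBC < 2000/µL | Value only | No |
| ALT/AST | Value, with documented reason | Yes |
| Serum creatinine | Value only | No |

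Six of the eight have no etiology-based stop, so their value-only restart conflicts with nothing. Two of the eight have one. In the ANC < 500/µL rule the restart and stop sentences are complements. In the ALT/AST rule they are not. The matching condition is therefore present in 1 of 2 rules now and would be in 2 of 2 after the edit. These counts are of rules, not subjects.

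**Step 3. Test the edit.** Adding the etiology condition to the restart sentence changes only the second row of the first table, where restart becomes not permitted. The other three rows keep their results.

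**Step 4. Cost in subjects.** Inputs from Protocol Section 7.6: 454 subjects in total; 54% Week 12 non-responders in SS1; 65% Week 12 responders in SS2; up to 8% dropout per 12 weeks; at least 96 subjects in each of SC1 and SC4. The 1:1 allocation is from Section 5.8.

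- Per sub-study: 454 / 2 = 227
- Retained through two 12-week periods: 0.92 × 0.92 = 0.8464
- SC1 at Week 24: 227 × 0.54 × 0.8464 = 103.8, which is 7.8 above 96
- SC4 at Week 24: 227 × 0.65 × 0.8464 = 124.9, which is 28.9 above 96
- SS1 non-response rate at which the SC1 margin disappears: 96 / (227 × 0.8464) = 0.4997, about 50%

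**The case against.** The strongest reply is that the text already gives one answer. Restart is permissive (*may*), discontinuation is directive (*should*), and the two stand close together in one paragraph, so they can be read as a rule and its exception. Section 5.5 then turns the direction into a *must*. A site that follows the whole cell and Section 5.5 stops the drug. This stands as an account of the intended meaning. It does not make the restart sentence state it: a site still has to combine two sections to learn that an express permission does not apply.

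Other safeguards exist. The etiology work-up is required. A confirmed value above 8 × ULN means contacting the sponsor's medical director. Subjects positive for hepatitis B core antibody have HBV DNA testing at set thresholds, with interruption and a hepatologist consultation if it is positive. Section 5.5 separately covers results that make continuation unsafe. Supplemental hepatic forms and study-team review add oversight. These bring the sponsor or a specialist into some of the most serious cases, but none of them makes restart depend on an identified etiology.

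It can also be said that Table 3 accepts restart after an unexplained abnormality elsewhere: a hemoglobin fall of at least 3.0 g/dL with no alternative etiology resumes on the value alone. That is true, but the hemoglobin rule has no etiology-based stop for its restart to contradict.

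Two limits remain. The number of affected subjects is unknown and probably small. The text of the Operations Manual (Appendix F) is not among the documents available here, so a clarification there cannot be ruled out; the governing table should still be consistent by itself.

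**Conclusion.** The concern holds. One of the four combinations of resolution and etiology, resolved with no alternative cause found, is subject to two opposite instructions in the same cell. Of the two Table 3 rules with an etiology-based stop, ALT/AST is the only one whose restart sentence omits the condition. Discontinuation is the better reading, so this is a conflict in the wording of a hepatic safety rule; the rule itself is not missing. It should be corrected because the words as they stand expressly allow re-exposure in a case where drug-induced injury is hard to exclude.

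The conclusion rests on the literal *or* between the discontinuation triggers and on the protocol text alone. No estimate, endpoint, analysis or sample-size figure changes.

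**What to change.** Amend only the restart sentence in the ALT/AST row. After the condition that values return to normal or Baseline, insert: *and an alternative etiology is identified*. This follows the ANC < 500/µL rule. Leave the discontinuation sentence, the documentation requirement and Section 5.5 as they are.

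The cost is one clause in the next amendment and a memo to sites, with no added visits, tests or analyses. Sites lose the apparent discretion to rechallenge after a resolved, unexplained elevation, and under Section 5.6 those subjects leave the study. At the planning assumptions the margins of 7.8 (SC1) and 28.9 (SC4) absorb a few such losses. The SC1 margin depends on the assumed 54% non-response and would be gone at about 50%.

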6.3 Other Safety Data Collection

Specific manifestations of AD (i.e., itching, excoriations, oozing, crusting, erythema, etc.) should not be reported as individual AEs if they are considered to be a worsening of the underlying disease; instead, worsening of AD should be reported as an AE.

7 STATISTICAL METHODS & DETERMINATION OF SAMPLE SIZE

7.1 Statistical and Analytical Plans

The statistical methods provided in this protocol will be focused on primary and secondary analyses. Complete and specific details of the statistical analysis will be described in the Statistical Analysis Plan (SAP).

7.2 Definition for Analysis Populations

The Intent to Treat (ITT) Populations for the efficacy analyses are defined as:

- ITT Population of SS1 in the double-blind period (ITT_1_SS1 Population) includes all subjects who are randomized into SS1.
- ITT Population of SS1 in the single-blind period (ITT_2_SS1 Population) includes all subjects who are randomized into SS1 at Baseline and continued into the single-blind period.
- ITT Population of SS2 in the double-blind period (ITT_1_SS2 Population) includes all subjects who are randomized into SS2.
- ITT Population of SS2 in the single-blind period (ITT_2_SS2 Population) includes all subjects who are randomized into SS2 at Baseline and continued into the single-blind period.

The Safety Populations for the safety analyses are defined as:

- Safety Population of SS1 in the double-blind period (Safety_1_SS1 Population) consists of all subjects who are randomized into SS1 and received at least 1 dose of study drug in the doubleblind period.
- Safety Population of SS1 in the single-blind period (Safety_2_SS1 Population) consists of all subjects who received at least 1 dose of study drug in the single-blind period of SS1.
- Safety Population of SS2 in the double-blind period (Safety_1_SS2 Population) consists of all subjects who are randomized into SS2 and received at least 1 dose of study drug in the doubleblind period.
- Safety Population of SS2 in the single-blind period (Safety_2_SS2 Population) consists of all subjects who received at least 1 dose of study drug in the single-blind period of SS2.
- Safety Population for all upadacitinib treatment (ALL_UPA Population) consists of all subjects who received at least 1 dose of upadacitinib in the study.

These populations will be used to provide a comprehensive summary of safety based on treatment received regardless of randomization.

